7.7. Quality Control and Quality Assurance

Data will be handled in accordance with data handling guidelines provided to sites. The Study Monitor and Data Manager will review data on an on-going basis and raise any discrepancies with site staff as required. Identified only by subject number, the data are deidentified at all times. All data transfers are fully documented.

Electronic data sets will provide an unmonitored subset of existing source data that will be subject to data validation. Site selection and training of site staff will ensure suitably qualified personnel are involved at every stage of the data gathering process.

The study coordinating center will be responsible for data handling and quality control. All data will be entered directly into the electronic data capture (EDC) system by appropriately trained and delegated site staff. Site selection and training of site staff will ensure suitably qualified personnel are involved at every stage of the data gathering process. The EDC will only collect data that is required as per the protocol and will be developed in line with the MACRO Utilisation SOP (DM-001). The data management team will review data on an on-going basis and raise any discrepancies with site staff as required, following the process set out in the Data Management Activities SOP (DM-002). Identified only by subject number, the data are processed in the pseudonymized format at all times. All data activities performed within the EDC will be captured by the system audit trail. Any transfers of data from the EDC will be documented following the processes as set out in the Data Management Activities SOP (DM-002).

The Neat ID Network team on behalf of the MAH will perform data review activities to assess protocol, consent and data quality issues. Any issues relating to study management quality performance will be reviewed and discussed during study team meetings. The Neat ID Network may decide to include this study in the annual audit schedule, as per Audit Activities SOP (QA-001). The audit conduct and reporting will be performed by the independent QA personnel and in accordance with the relevant regulations, the protocol and the applicable Standard Operating Procedures.

Site selection and training of site staff will ensure suitably qualified personnel are involved at every stage of the data gathering process.

7.8. Limitations of the research methods

Limitations of this study are common to non-randomized, non-interventional observational cohort studies. This is a study of routine clinical care and reflects treatment practice across NEAT-ID Network clinical sites. Confounding by indication, whereby persons are selected for specific regimens, cannot be ruled out. While the study aims to include a target of at least 500 individuals initiating CAB LA for PrEP, market uptake of the regimen and individuals' willingness to participate will dictate how quickly data will be collected.

Follow-up of study participants through the end of the follow-up period after discontinuation of CAB LA for PrEP or after HIV acquisition will increase the potential for loss to follow-up as would be expected, in a real-world setting. The results from this study should be interpreted cautiously, with careful consideration given to the limitations of the observational study design.

8. **PROTECTION OF HUMAN SUBJECTS**

8.1. Ethical approval and subject consent

Before the start of data collection, this protocol and any accompanying material to be provided to the participants (subject information sheets, or descriptions of the study used to obtain informed consent) will be submitted to an Ethics Committee (EC) in the relevant countries. The participating clinical sites will not begin any study activities until approval from the EC has been documented and the Sponsor (MAH) has provided as an activation letter to the clinical site investigator.

Any subsequent amendments that require review by the EC will not be implemented until the EC grants the amendments a favourable opinion which will be disseminated to the investigator and sites (NOTE: amendments may also need to be reviewed and accepted by the regulatory agencies and/or local EC departments before they can be implemented in practice at sites). In accordance with the requirements of the EC, an annual progress report will be submitted as needed to the EC. NEAT-ID team will notify the EC in each country with a participating site of the end of the study. If the study is ended prematurely, NEAT-ID will notify the EC, including the reasons for the premature termination.

8.2. Subject confidentiality

All investigators and study site staff will comply with the requirements of the current Data Protection Regulations with regards to the collection, storage, processing and disclosure of personal information and will uphold the Regulation's core principles.

• Only deidentified data is reported to the central study database. Identifiable individual information (held only by the site investigator in routine medical records) will be kept secure at all times and maintained in line with local applicable standard operating procedures. Access to this will be to the minimum number of individuals necessary for quality control, and audit reasons. There will be no entry of any directly identifiable data into the study database at any time.

9. *LEGAL BASIS FOR PROCESSING INDIVIDUAL HUMAN DATA

The authors confirm that study data is Individual Human Data (IHD) not owned by ViiV Healthcare, but that the proposed use of the IHD aligns with the 'purpose of use' outlined in the source contract and/or the terms and conditions of use of the data source and it will comply with any specified prohibitions of use.

10. MANAGEMENT AND REPORTING OF ADVERSE EVENTS/ADVERSE REACTIONS

Collection of adverse events/reactions (Solicited Events)

The purpose of the study is to monitor exposure to Apretude and to evaluate DILI and HSRs. For Apretude, pre-defined safety events of interest, DILI and HSRs, will be systematically recorded in aggregate. These will be summarised in interim, if applicable, and final study reports. This study is based on secondary use of existing health data and as such Individual Case Safety Reporting (ICSRs) to regulatory agencies is not required.

Reporting of adverse events/reactions (Spontaneous Events)

The purpose of the study is to monitor individuals exposed to Apretude and to evaluate pre-defined safety events in aggregate. There is no potential to collect serious and nonserious spontaneous AEs, pregnancy exposures, or incidents related to any GSK/ViiV product during the conduct of this research, as the minimum criteria of identifiable individuals, reporter, exposure and event, needed to collect and report individual case safety reports are not present in the data source. The study is based on secondary anonymised healthcare data which lack an identifiable individual and reporter and are insufficient to establish attribution between a potential safety event and an individual using a GSK/ViiV product. This study is based on data previously collected for other purposes e.g., routine healthcare encounters. As such, there is no requirement for the collection and reporting of Individual Case Safety Reports (ICSRs).

This is a non-interventional study based on secondary use of data collected to support clinical care. The study uses deidentified data, and there is no potential to collect individual level data on serious and non-serious adverse events (AEs), pregnancy exposures, device deficiencies and device related events or incidents related to any ViiV Healthcare product during the conduct of this research, as the minimum criteria needed to report AEs, pregnancy exposures, and incidents are not collected. Specifically, the data are insufficient to establish attribution between a potential safety event and an individual

using a ViiV Healthcare product as the study design is to analyse deidentified, secondary data collected from individual medical records. Therefore, a safety management plan will not be developed.

Participating clinical sites and health care providers will be strongly encouraged to report all pregnancies occurring while using CAB LA for PrEP, prospectively (i.e., reported prior to the outcome of pregnancy is known) to the Antiretroviral Pregnancy Registry ([contact] or www.APRegistry.com).

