DILI case definition: Determination of suspected or potential DILI will be based on liver chemistry criteria (ALT, BILI and ALP) in addition to all relevant clinical information based on Aithal et al, 2011.⁵ An independent adjudication committee will review all potential and suspected cases of DILI that meet the liver chemistry criteria for DILI for drug attribution to CAB for PrEP. The adjudication committee will be provided with all relevant clinical information collected from data in the health records, to enable a comprehensive review and assessment of potential DILI attributed to CAB PrEP.

Liver chemistry criteria for DILI including any one of the following:

- a) More than or equal to fivefold elevation above the upper limit of normal (ULN) for ALT
- b) More than or equal to twofold elevation above the ULN for ALP (particularly with accompanying elevations in concentrations of 5'nucleotidase or γ-glutamyl transpeptidase in the absence of known bone pathology driving the rise in ALP level)
- c) More than or equal to threefold elevation in ALT concentration and simultaneous (within +/- 2 weeks) elevation of BILI concentration exceeding 2× ULN after starting CAB LA PrEP at 6, 12, 24, 36, and >36 months after initiation

If the person has had previous liver injury and hence abnormal LCT prior to starting CAB for PrEP, ULN is replaced by the mean baseline values obtained at baseline, (i.e., 5× baseline for ALT, 2x baseline for ALP and 2× baseline for BILI with associated 3× baseline elevation in ALT). Classification of the clinical severity of DILI involves use of the peak measured values for each of the biochemical parameters during the course of DILI.

Cases of suspected or potential DILI with attribution to CAB for PrEP will be tabulated according to the DILI severity grade as below:

Description of HSR: Signs and symptoms of HSR reported with INSTIs include, but are not limited to, severe rash, or rash accompanied by fever, general malaise, fatigue, muscle or joint aches, blisters, oral lesions, conjunctivitis, facial oedema, hepatitis, eosinophilia or angioedema. Clinical status, including liver transaminases, will be considered and frequency of HSRs will be assessed at 6, 12, 24, 36, and >36 months after study start.

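### Section 10 denies individual-level adverse event data and attribution without exception, while Objective 4 rests on subject-level DILI and HSR cases attributed to CAB from the same records

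*Protocol*

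**What the plan says.** Section 10 opens with solicited events, where "pre-defined safety events of interest, DILI and HSRs, will be systematically recorded in aggregate". Under spontaneous events it describes the source as anonymised healthcare data and lists exposure and event among the case-report criteria that the source lacks. Its closing text says that "there is no potential to collect individual level data on serious and non-serious adverse events (AEs" (the list goes on to pregnancy exposures and device events). It adds that "the data are insufficient to establish attribution between a potential safety event and an individual" using the sponsor's product, because "the study design is to analyse deidentified, secondary data collected from individual medical records". From this it concludes that no safety management plan will be written.

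Section 7.3.2 treats DILI as hepatotoxicity related to CAB. The committee is to "review all potential and suspected cases of DILI that meet the liver chemistry criteria for DILI for drug attribution to CAB for PrEP", using the clinical information held in the health records, and "Cases of suspected or potential DILI with attribution to CAB for PrEP will be tabulated according to the DILI severity grade". Potential HSR cases go to the same committee for confirmation, again from health-record information.

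Section 7.5 collects injection dates with clinical and laboratory data, identified by subject number. Section 7.6.1 (Objective 4) reports how many individuals have DILI or HSR, and how many stop CAB because of either. Section 7.7 says that "the data are processed in the pseudonymized format at all times".

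**The concern.** The two parts of the protocol describe one data source in opposite terms. Section 10 says that the source cannot tie a safety event to a user of the product. Section 7.3.2 asks a committee to do that, case by case, and makes the result part of the DILI outcome.

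Hepatotoxicity monitoring is in the study title, and Section 11.1 submits the protocol for regulatory endorsement. A reader who takes Section 10 at its word would doubt the adjudicated DILI and HSR results. A reader who takes Section 7.3.2 at its word would find that the reason given for omitting a safety management plan does not describe the data.

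A related analysis question is whether the reported DILI frequency should depend only on attribution made from routine records. Section 7.3.3 collects liver tests only when they were done, and ALP, itself one of the liver chemistry criteria, only where available.

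**Working it through.** No figure in the protocol is at issue and no arithmetic applies. The check is a comparison of the statements, property by property.

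1. **Level of the data.** Section 10: solicited events in aggregate, and no potential for individual-level adverse event data. Sections 7.3.2 and 7.6.1: individual cases, each reviewed by the committee, DILI graded for severity, and counts of individuals who discontinue because of an event. Taken as a statement about reporting, aggregate recording is compatible with case review. The denial of individual-level data is not.

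2. **Exposure and event in the same person.** Section 10 lists both among the criteria absent from the source. Section 7.5 collects injection dates together with laboratory and clinical data under one subject number, so both are held per person.

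3. **Attribution.** Section 10: the data do not suffice. Section 7.3.2: "An independent adjudication committee will review all potential and suspected cases of DILI that meet the liver chemistry criteria", expressly for attribution to CAB. The HSR text likewise has the committee assess potential HSRs attributed to CAB.

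4. **Source.** Section 10 gives as its reason that the data are deidentified and come from individual medical records. The committee works from health-record information too. The reason therefore covers the adjudicated endpoints as much as any other event. Removing names does not in itself break the link between a subject's injections and that subject's liver tests.

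5. **Privacy status.** Section 10: anonymised. Section 7.7: pseudonymised. Section 8.2 adds that the site investigator holds the identifiable information. These are different states of the data.

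6. **What reaches the tables.** The severity table in Section 7.3.2 is limited to DILI attributed to CAB, and that section's outcome list equates DILI with CAB-related hepatotoxicity. Objective 4 in Section 7.6.1 states no attribution condition of its own. The protocol names no committee category for a case whose information is too thin to judge, and does not say whether such a case is counted.

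Items 2 to 5 conflict as written. Item 1 conflicts in part. Item 6 is an ambiguity in what is counted, not a contradiction.

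**The case against.** The strongest reply is that the attribution sentence stands under the spontaneous-events heading. The text around it concerns the minimum criteria for individual case safety reports, while DILI and HSR are dealt with separately as solicited events. On that reading Section 10 only explains why case reports are not filed, and aggregate describes how results are reported. This is probably the intent, and much of the section can be read so. But the closing text speaks of the data as a whole and of any potential safety event, makes no exception for DILI or HSR, gives a reason that applies equally to them, and draws a conclusion for the whole study.

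It can also be said that handling of unclassifiable cases belongs in a committee charter or analysis plan, neither of which is at hand. That is fair as to detailed rules. It does not remove the restriction to attributed cases, which the protocol itself sets.

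A reader might infer that the DILI and HSR endpoints cannot be measured. The documents do not support this, because Sections 7.3.2, 7.3.3 and 7.5 consistently provide for subject-level data. A reader might also infer that the reported DILI frequency is biased low. Nothing in the protocol says that poorly documented cases are dropped, and sparse records could also lead to over-attribution. No loss rate or true incidence is given from which a bias could be computed.

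**Conclusion.** The point holds as an internal inconsistency. Section 10 makes blanket statements about the data that Sections 7.3.2, 7.5, 7.6.1 and 7.7 contradict. It bears on both Objective 4 endpoints, DILI and HSR, and on discontinuation due to either, at 6, 12, 24 and 36 months and over the whole follow-up. It also bears on the stated ground for having no safety management plan. Whether such a plan or individual case reports are required is a regulatory question that the documents do not settle, and this point does not claim that they are.

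The size cannot be expressed as a number. Under-reporting of DILI is possible if cases with thin records fail attribution and are left out. That depends on committee rules and record completeness that the protocol does not give. The conclusion assumes that the committee works from the same medical-record source that Section 10 describes, which is how both sections read.

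**What to change.** In Section 10, limit the statements on individual-level data and attribution to the identifiability of patient and reporter for individual case reports, and say that they do not apply to the adjudicated DILI and HSR endpoints. Change the description of the data as anonymised to agree with Section 7.7. Have the sponsor re-examine the reason given for having no safety management plan, since the present one rests on the statements being narrowed.

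In Sections 7.3.2 and 7.6.1 (Objective 4), tabulate every case meeting the liver chemistry criteria and every potential HSR, then split each by committee category, including one for insufficient information. The severity table of attributed DILI can stay. This gives a frequency that does not depend on attribution alone, although it still depends on liver tests having been done.

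The cost is a rewording of Section 10, reviewed by the sponsor's safety group, and one extra column in the DILI and HSR tables. No new data collection is needed.

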11. PLANS FOR DISSEMINATING AND COMMUNICATING STUDY RESULTS

11.1. Target Audience

This study-specific protocol will be submitted for EMA's review and endorsement. The study will start once CAB LA for PrEP is commercially available in Europe and is expected to continue through 2029 or later. Annual interim reports with cumulative data will be submitted and a final report is expected to be submitted in July 2030.

